1.1 Does the protocol specify timelines for				
1.1.1 Start of data collection ³				4.10,6
1.1.2 End of data collection ⁴				4.10,6
1.1.3 Study progress report(s)				4.10,6
1.1.4 Interim progress report(s)				4.10,6
1.1.5 Registration in the EU PAS register				4.10,6
1.1.6 Final report of study results.				4.10,6

Comments:

Section 2: Research question	Yes	No	N/A	Section Number
2.1 Does the formulation of the research question and objectives clearly explain:				
2.1.1 Why the study is conducted? (e.g. to address an important public health concern, a risk identified in the risk management plan, an emerging safety issue)				7
2.1.2 The objective(s) of the study?				8.2
2.1.3 The target population? (i.e. population or subgroup to whom the study results are intended to be generalised)				8.1
2.1.4 Which hypothesis(-es) is (are) to be tested?				
2.1.5 If applicable, that there is no a priori hypothesis?				7

Comments:

Section 3: Study design	Yes	No	N/A	Section Number
3.1 Is the study design described? (e.g. cohort, case-control, cross-sectional, new or alternative design)				9.1

³ Date from which information on the first study is first recorded in the study dataset or, in the case of secondary use of data, the date from which data extraction starts.

⁴ Date from which the analytical dataset is completely available.

Section 3: Study design	Yes	No	N/A	Section Number
3.2 Does the protocol specify whether the study is based on primary, secondary or combined data collection?				9.2,9.4
3.3 Does the protocol specify measures of occurrence? (e.g. incidence rate, absolute risk)				9.7
3.4 Does the protocol specify measure(s) of association? (e.g. relative risk, odds ratio, excess risk, incidence rate ratio, hazard ratio, number needed to harm (NNH) per year)				9.7
3.5 Does the protocol describe the approach for the collection and reporting of adverse events/adverse reactions? (e.g. adverse events that will not be collected in case of primary data collection)				11

Comments:

--

Section 4: Source and study populations	Yes	No	N/A	Section Number
4.1 Is the source population described?				9.2.1
4.2 Is the planned study population defined in terms of:				9.2.1.4
4.2.1 Study time period?				8.2
4.2.2 Age and sex?				9.2.1
4.2.3 Country of origin?				9.2.1
4.2.4 Disease/indication?				9.2.1.4
4.2.5 Duration of follow-up?				9.2.1.4
4.3 Does the protocol define how the study population will be sampled from the source population? (e.g. event or inclusion/exclusion criteria)				9.2.1.1

Comments:

No sex or seasonality limitations. Patients ≥ 65 years and those with hypertension, diabetes, or cardiovascular disease diagnostic codes will be subgroups of interest for the analysis.

Section 5: Exposure definition and measurement	Yes	No	N/A	Section Number
5.1 Does the protocol describe how the study exposure is defined and measured? (e.g. operational details for defining and categorising exposure, measurement of dose and duration of drug exposure)				9.3.2
5.2 Does the protocol address the validity of the exposure measurement? (e.g. precision, accuracy, use of validation sub-study)				9.3.4

Section 5: Exposure definition and measurement	Yes	No	N/A	Section Number
5.3 Is exposure classified according to time windows? (e.g. current user, former user, non-use)				9.3.2
5.4 Is exposure classified based on biological mechanism of action and taking into account the pharmacokinetics and pharmacodynamics of the drug?				

Comments:

--

Section 6: Outcome definition and measurement	Yes	No	N/A	Section Number
6.1 Does the protocol specify the primary and secondary (if applicable) outcome(s) to be investigated?				9.2.1.2
6.2 Does the protocol describe how the outcomes are defined and measured?				9.2.1.2
6.3 Does the protocol address the validity of outcome measurement? (e.g. precision, accuracy, sensitivity, specificity, positive predictive value, prospective or retrospective ascertainment, use of validation sub-study)				9.3.4
6.4 Does the protocol describe specific endpoints relevant for Health Technology Assessment? (e.g. HRQoL, QALYs, DALYS, health care services utilisation, burden of disease, disease management)				

Comments:

--

Section 7: Bias	Yes	No	N/A	Section Number
7.1 Does the protocol describe how confounding will be addressed in the study?				9.3.2
7.1.1. Does the protocol address confounding by indication if applicable?				
7.2 Does the protocol address:				
7.2.1. Selection biases (e.g. healthy user bias)				9.9
7.2.2. Information biases (e.g. misclassification of exposure and endpoints, time-related bias)				9.9
7.3 Does the protocol address the validity of the study covariates?				9.3.4

Comments:

--

Section 8: Effect modification	Yes	No	N/A	Section Number
8.1 Does the protocol address effect modifiers? (e.g. collection of data on known effect modifiers, sub-group analyses, anticipated direction of effect)				9.3.2

Comments:

Section 9: Data sources	Yes	No	N/A	Section Number
9.1 Does the protocol describe the data source(s) used in the study for the ascertainment of:				
9.1.1 Exposure? (e.g. pharmacy dispensing, general practice prescribing, claims data, self-report, face-to-face interview, etc.)				9.4
9.1.2 Outcomes? (e.g. clinical records, laboratory markers or values, claims data, self-report, patient interview including scales and questionnaires, vital statistics, etc.)				9.4
9.1.3 Covariates?				9.4
9.2 Does the protocol describe the information available from the data source(s) on:				
8.2.1 Exposure? (e.g. date of dispensing, drug quantity, dose, number of days of supply prescription, daily dosage, prescriber)				4.7
8.2.2 Outcomes? (e.g. date of occurrence, multiple event, severity measures related to event)				4.7
8.2.3 Covariates? (e.g. age, sex, clinical and drug use history, co-morbidity, co-medications, life style, etc.)				4.7
9.3 Is a coding system described for:				
9.3.1 Exposure? (e.g. WHO Drug Dictionary, Anatomical Therapeutic Chemical (ATC) Classification System)				4.7
9.3.2 Outcomes? (e.g. International Classification of Diseases (ICD)-10, Medical Dictionary for Regulatory Activities (MedDRA))				4.7
9.3.3 Covariates?				4.7
9.4 Is a linkage method between data sources described? (e.g. based on a unique identifier or other)				4.7

Comments:

Section 10: Analysis plan	Yes	No	N/A	Section Number
10.1 Is the choice of statistical techniques described?				4.9
10.2 Are descriptive analyses included?				4.9
10.3 Are stratified analyses included?				4.9
10.4 Does the plan describe methods for adjusting for confounding?				4.9

Section 10: Analysis plan	Yes	No	N/A	Section Number
10.5 Does the plan describe methods for handling missing data?				4.9
10.6 Is sample size and/or statistical power estimated?				4.8

Comments:

Section 11: Data management and quality control	Yes	No	N/A	Section Number
11.1 Does the protocol provide information on data storage? (e.g. software and IT environment, database maintenance and anti-fraud protection, archiving)				9.6
11.2 Are methods of quality assurance described?				9.8
11.3 Is there a system in place for independent review of study results?				9.8

Comments:

Section 12: Limitations	Yes	No	N/A	Section Number
12.1 Does the protocol discuss the impact on the study results of:				
12.1.1 Selection bias?				9.9
12.1.2 Information bias?				9.9
12.1.3 Residual/unmeasured confounding? (e.g. anticipated direction and magnitude of such biases, validation sub-study, use of validation and external data, analytical methods)				9.9
12.2 Does the protocol discuss study feasibility? (e.g. study size, anticipated exposure, duration of follow-up in a cohort study, patient recruitment)				9.3.3

Comments:

Section 13: Ethical issues	Yes	No	N/A	Section Number
13.1 Have requirements of Ethics Committee/ Institutional Review Board been described?				10
13.2 Has any outcome of an ethical review procedure been addressed?				
13.3 Have data protection requirements been described?				9.8

Comments:

Section 14: Amendments and deviations	Yes	No	N/A	Section Number
14.1 Does the protocol include a section to document amendments and deviations?				5

Comments:

Section 15: Plans for communication of study results	Yes	No	N/A	Section Number
15.1 Are plans described for communicating study results (e.g. to regulatory authorities)?				12.1
15.2 Are plans described for disseminating study results externally, including publication?				12.2

Comments:

Name of the main author of the protocol: ██████████

Date: 8/Nov/2022

Signature: ██████████

ANNEX 3. ADDITIONAL INFORMATION

List of Read, ICD and SNOMED Codes to Identify Patients with IBS-C

Table 4. Read Codes for the Identification of IBS and Constipation

Read Code	Description	Comments
J521100	Irritable bowel syndrome characterised by constipation	Preferred code.
J521000	IBS with diarrhoea	To be used as exclusion criteria
14CF.00	History of irritable bowel syndrome (IBS)	To identify potential prevalent cases
Eu45324	Psychogenic IBS	Unfrequently used, check for constipation
J521.00	Irritable colon-IBS	Preferred code, check for constipation
J521.13	Spastic colon	Unfrequently used, check for constipation
J521.11	Irritable bowel syndrome	Preferred code, check for constipation
J521200	IBS characterized by alternating bowel habit	Preferred code, check for constipation
19C..11	Constipation symptom	Preferred code, combined with IBS
19C..00	Constipation	Preferred code, combined with IBS
19C2.00	Constipated	Unfrequently used, combined with IBS
19CZ.00	Constipation NOS	Unfrequently used, combined with IBS
J520z00	Constipation NOS	Third choice, combined with IBS
J520.00	Constipation – functional	Second choice, combined with IBS
J520100	Chronic constipation with overflow	Unfrequently used, combined with IBS
J520000	Acute constipation	Unfrequently used, combined with IBS
J520200	Chronic constipation without overflow	Unfrequently used, combined with IBS
J520300	Drug induced constipation	Unfrequently used, combined with IBS
E264500	Psychogenic constipation	Unfrequently used, combined with IBS
J520y00	Other specified constipation	Unfrequently used, combined with IBS
1962.00	Colicky abdominal pain	Second choice as code in IBS
1971.00	Central abdominal pain	Third choice as code in IBS
1972.00	Epigastric pain	Third choice as code in IBS
196..00	Type of GIT pain	Unfrequently used
196..11	Abdominal pain type	Unfrequently used
1968.00	Abdominal discomfort	Third choice as code in IBS
1969.00	Abdominal pain	Second choice as code in IBS
197..13	Site of abdominal pain	Unfrequently used
197A.00	Generalised abdominal pain	Second choice as code in IBS
197C.00	Lower abdominal pain	Third choice as code in IBS
197Z.00	Site of GIT pain NOS	Unfrequently used
1963.00	Non-colicky abdominal pain	Unfrequently used

196Z.00	Type of GIT pain NOS	Unfrequently used
196..12	Type of GIT pain - symptom	Unfrequently used
1976.00	Right flank pain	Unfrequently used
1975.00	Left flank pain	Unfrequently used
197..11	Flank pain	Unfrequently used
197..12	Iliac fossa pain	Unfrequently used
1977.00	Right iliac fossa pain	Unfrequently used
1978.00	Left iliac fossa pain	Unfrequently used
197B.00	Upper abdominal pain	Unfrequently used
197D.00	Right upper quadrant pain	Unfrequently used
1974.00	Right subcostal pain	Unfrequently used
197..00	Site of GIT pain	Unfrequently used
197..14	Subcostal pain	Unfrequently used
1973.00	Left subcostal pain	Unfrequently used
197A.11	General abdominal pain symptom	Unfrequently used
R090400	[D] Abdominal cramps	Unfrequently used
R090.00	[D] Abdominal pain	Unfrequently used
R090500	[D] Epigastric pain	Unfrequently used
R09E00	[D] Recurrent acute abdominal pain	Unfrequently used
R090z00	[D] Abdominal pain NOS	Unfrequently used
R090100	[D] Abdominal colic	Unfrequently used
R090700	[D] Hypochondrial pain	Unfrequently used
R090400	[D] Abdominal cramps	Unfrequently used
R090N00	[D] Nonspecific abdominal pain	Unfrequently used
R090J00	[D] Right upper quadrant pain	Unfrequently used
R090H00	[D] Upper abdominal pain	Unfrequently used
R090900	[D] Pain in right iliac fossa	Unfrequently used
R090600	[D] Umbilical pain	Unfrequently used
R090A00	[D] Pain in left iliac fossa	Unfrequently used
R090000	[D] Abdominal tenderness	Unfrequently used
R090K00	[D] Left upper quadrant pain	Unfrequently used
R090y00	[D] Other specified abdominal pain	Unfrequently used
R090L00	[D] Left lower quadrant pain	Unfrequently used
R090311	[D] Right lower quadrant pain	Unfrequently used
1961.00	No abdominal pain	To be used as exclusion criteria
19A..00	Abdominal distension symptom	Second choice as code in IBS
19A3.00	Abdomen feels distended	Unfrequently used
19A2.00	Abdomen feels bloated	Unfrequently used
19AZ.00	Abd. Distension symptom NOS	Unfrequently used

19A4.00	Abdomen feels swollen	Unfrequently used
19B..12	Bloating symptom	Second choice as code in IBS
19B..15	Wind symptom	Unfrequently used
19B2.00	Excessive flatulence	Unfrequently used
19B..14	Flatulence symptom	Unfrequently used
19B..00	Flatulence/wind	Unfrequently used
19BZ.00	Wind NOS	Unfrequently used
R073400	[D] Bloating	Third choice as code in IBS
R073000	[D] Flatulence	Unfrequently used
R073.00	[D] Flatulence, eructation, and gas pain	Third choice as code in IBS
R073300	[D] Abdominal distension, gaseous	Unfrequently used
R073z11	[D] Wind	Unfrequently used
R073200	[D] Gas pain (abdominal)	Unfrequently used
R073z00	[D] Flatulence, eructation and gas pain NOS	Unfrequently used
19EA.00	Change in bowel habit	Unfrequently used
19EA.11	Altered bowel habit	Unfrequently used
R078.00	[D] Change in bowel habit	Unfrequently used
R121200	[D] Mucus in stool	Unfrequently used
4763.00	Faeces: mucous present	Unfrequently used
19EH.00	Mucus in faeces	Unfrequently used
198..00	Nausea	Second choice as code in IBS
1982.00	Nausea present	Unfrequently used
198..12	Nausea symptoms	Third choice as code in IBS
198..11	C/O - nausea	Unfrequently used
198Z.00	Nausea NOS	Unfrequently used
R070000	[D] Nausea	Unfrequently used
R070.00	[D] Nausea and vomiting	Unfrequently used
R093000	[D] Abdominal swelling	Unfrequently used
J16y411	Flatulent dyspepsia	Unfrequently used
19D..12	Anal symptoms	Unfrequently used
19D..11	Tenesmus symptom	Unfrequently used
19D..00	Tenesmus	Unfrequently used
19D2.00	Tenesmus present	Unfrequently used
19DZ.00	Tenesmus NOS	Unfrequently used
19E..11	Faeces symptom	Unfrequently used
19E..12	Motions – symptom	Unfrequently used
19E..00	Faeces/motions – symptoms	Unfrequently used

Abbreviations: IBS irritable bowel syndrome; IBS C IBS predominately with constipation; NOS unspecified

Patients with IBS will be identified through the following criteria:

- Code J521100 (Irritable bowel syndrome characterised by constipation)
- One or more codes for IBS among the following: J521.00, J521.11, J521.13, Eu45324, 14CF.00.
- Alternatively, a combination of a code of abdominal pain or discomfort (in gray background and regular font) and at least two codes among those reported as "second choice as code in IBS", "third choice as code in IBS" or "unfrequently used" (in *italics* and gray background).

Patients with only 14CF.00 will identify as prevalent IBS-C patients since the diagnosis date is uncertain.

In addition to patients with code J521100, patients with IBS-C will be identified through the following criteria:

- Patient with IBS as specified above and one preferred code including the term "constipation"

Table 5. ICD-10 Codes for the Identification of IBS and Constipation

909031000006119	[RFC] Constipation
982721000006114	Constipation
131671000006119	Spurious diarrhoea - overflow
196858012	Spurious diarrhoea
441433010	Difficulty in ability to defaecate
5878931000006114	Difficult defaecation
5878951000006119	Difficulty in defaecating

A Patient will be said to have IBS if there is a SNOMED code from IBS 1 code lists in the medical records OR if there is a SNOMED code from IBS 2 code lists AND 2 or more codes from IBS 3 code lists ever.

A patient with IBS identified from the SNOMED code lists above will be said to have IBS-C if they have any of the codes from [Table 10](#).

List of Read Codes, ICD codes and SNOMED codes to Identify the Safety Endpoint: SCD

Published literature from the candidate databases on diarrhoea and its complications is limited. Still, the identification of these endpoints is possible using a set of codes to capture diarrhoea, electrolyte imbalances, etc. One concern is that conditions such as electrolyte imbalances are not necessarily only complications of diarrhoea; the International Classification of Diseases and Related Health Problems, 10th Revision, Clinical Modification (ICD-10-CM) and Read codes to identify these conditions are unspecific in this respect (i.e., codes for electrolyte imbalance and others do not reflect whether the condition is secondary to diarrhoea). We suggest using combinations of codes for diarrhoea and each of these conditions to ensure that diarrhoea-related events are identified as such (we will only consider those diarrhoea complications occurring between the diarrhoea diagnosis date and 45 days afterwards). Below is a preliminary list of codes to be used.

Diarrhoea

Diarrhoea is the condition of passing three or more loose or liquid bowel movements per day, or more than is normal for the individual (World Health Organization [WHO], 2012). Loss of fluids through diarrhoea can cause dehydration and electrolyte imbalances.

Lists of Read ([Table 11](#)), ICD-9 ([Table 12](#)) and SNOMED ([Table 13](#)) codes to identify diarrhoea episodes are included below.

Table 11. Read Codes to Identify Episodes of Diarrhoea

Read Code	Description	Specific
19F..11	Diarrhoea	
19F..00	Diarrhoea symptoms	
19FZ.11	Diarrhoea and vomiting, symptom	
19F2.00	Diarrhoea	
19G..00	Diarrhoea and vomiting	
A083.11	Diarrhoea and vomiting -? infect	No
A083.00	Diarrhoea of presumed infectious origin	No
19FZ.00	Diarrhoea symptom NOS	
J525.00	Functional diarrhoea	
A076.11	Viral diarrhoea	No
19F4.00	Toddlers diarrhoea	No
A082.00	Infectious diarrhoea	No
A082z00	Infectious diarrhoea NOS	No
J4...13	Non-infective diarrhoea	
A074311	Diarrhoea due to campylobacter jejuni	No
E264300	Psychogenic diarrhoea	
J4zz.11	Diarrhoea – presumed non-infectious	
J4z..11	Presumed non-infectious diarrhoea	
J4z..00	Non-infective gastroenteritis NOS	
A082100	Epidemic diarrhoea	No
Eu45317	[X] Psychogenic diarrhoea	
A074011	Diarrhoea due to staphylococcus	No
Ayu0H00	[X] Diarrhoea and gastroenteritis of presumed infectious origin	No
A074012	Diarrhoea due to staphylococcal toxin	No
A074111	Diarrhoea due to pseudomonas pyocyanea	No
19F. 12	Loose stools	
R077100	[D] Stools loose	
4743.00	Faeces consistency: semi-fluid	
4744.00	Faeces consistency: fluid	
E264311	Spurious diarrhoea	
19F3.00	Spurious (overflow) diarrhoea	
J43z.11	Chronic diarrhoea	
J43z.00	Other non-infective gastroenteritis and colitis NOS	
A082000	Dysenteric diarrhoea	No
J433.11	Dietetic diarrhoea	No
J432.11	Allergic diarrhoea	No

Abbreviations: NOS unspecified

Table 12. ICD Codes to Identify Episodes of Diarrhoea

ICD-9-CM	2013 ICD-9-CM Additional Description	Direct or Approximate Conversion to ICD-10-CM
787.91 Diarrhoea	Abnormal frequency and fluidity of faeces Increased liquidity or decreased consistency of faeces, such as running stool; faecal consistency is related to the ratio of water-holding capacity of insoluble solids to total water, rather than the amount of water present; diarrhoea is not hyperdefecation or increased faecal weight. Passage of loose, unformed stools, a condition of frequent and watery bowel movements	K52.2 Allergic and dietetic gastroenteritis and colitis K52.89 Other specified non-infective gastroenteritis and colitis R19.7 Diarrhoea, unspecified
009.2 Infectious diarrhoea		A09 Infectious gastroenteritis and colitis, unspecified
009.3 Diarrhoea of presumed infectious origin		A09
564.5 Functional diarrhoea		K59.1 Functional diarrhoea
558.9 Other and unspecified non-infectious gastroenteritis and colitis		K52.9 Non-infective gastroenteritis and colitis, unspecified
558.2 Toxic gastroenteritis and colitis		K52.1 Toxic gastroenteritis and colitis

ICD-9-CM	2013 ICD-9-CM Additional Description	Direct or Approximate Conversion to ICD-10-CM
558.42 Eosinophilic colitis		K52.8 Other specified non-infective gastroenteritis and colitis
535.70 Eosinophilic gastritis, without mention of haemorrhage		
535.71 Eosinophilic gastritis, with haemorrhage		
558.41 Eosinophilic gastroenteritis		

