9.2.1.1 INCLUSION/EXCLUSION CRITERIA IN THE IBS-C COHORT

Patients in the study will be required to meet the following inclusion criteria:

- Patient meets IBS-C criteria, as identified through the combination of IBS and constipation codes, (please refer to Section 9.3.4 *Validation of the Diagnosis and Safety Endpoints* below and Annex 3) anytime during the study period
- Patient has at least 12 months of computerised records prior to IBS-C cohort entry date
- Patient meets 'acceptable' criteria from CPRD (the patient is permanently registered at the practice or the PCP and has a valid year of birth and gender) at IBS-C cohort entry date (UK); no equivalent criteria for Spain or Sweden.
- Patient is active (i.e., alive and permanently registered at a practice (UK) or a PCP office (Spain) or the national register (Sweden)) at IBS-C cohort entry date

The following exclusion criteria will apply:

- Patient has no follow-up time (for example, transfers out or dies on the date IBS-C criteria are first fulfilled)
- The practice's up-to-standard (UTS) date in CPRD GOLD is later than the IBS-C cohort entry date (UK); no equivalent criteria for CPRD Aurum, Spain or Sweden*.

*Note: For CPRD GOLD, practices meeting pre-defined quality control standards for completeness, continuity, and plausibility are registered as UTS since the date those standards are met. 'Acceptable' and 'up to standard' are two quality flags that will be taken into account when selecting the study cohort in CPRD GOLD in the UK. In CPRD Aurum, there is no equivalent flag for UTS, therefore, only the 'acceptable' flag will be used for cohort selection. In Spain, no such flags exist but the SIDIAP confirmed that given the study will be performed using data from 2014 onwards, all the data included is of good quality for research purposes. In Sweden, the data received has already been through a quality control by the National Board of Health and Welfare. This control includes checking that compulsory variables like personal registration number, hospital, and main diagnosis are reported, and the validity of all variables values tested. Therefore, no additional changes in the inclusion and exclusion criteria will be needed for Spain and Sweden.

Patients meeting IBS-C inclusion criteria (and not meeting exclusion criteria) at the beginning of the study period (see below) will be prevalent IBS-C patients. Patients meeting IBS-C inclusion criteria thereafter will be incident IBS-C patients.

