In response to the MAH's proposal, in the preliminary assessment report for the PASS protocol amendment submission (3rd Oct 2022), PRAC requested the MAH to extend the UK observational period up to the most recent possible date in order to include all available data and to revise the data collection period in the milestones accordingly, without further postponement of the final report (Q3 2023). The MAH contacted CPRD to confirm next steps for data extraction and validation study rerun. CPRD required that the MAH submits a new protocol to the CPRD review committee before requesting the new datasets and re-running the validation study. This is due to the change of dataset from CPRD GOLD to CPRD GOLD and CPRD Aurum, and the change of the observational period. The MAH submitted a new protocol to CPRD in April 2023 and expected to receive approval and the new datasets in Q3 2023. However, the actual process from application submission to data access took almost 12 months and the final data cut was eventually delivered in March 2024. The identification of new potential SCD cases as well as the initiation of validation activities have been completed in Q2 2024.

The validation of the diagnosis and SCD cases ended in Q2 2020 in Spain and expected to end in Q3 2024 in the UK. There is no validation study in Sweden. This study period is expected to allow for sufficient follow-up (long-term safety assessment) for those enrolled during the first period after linaclotide launch and for any subpopulations of interest (those with increased risk of SCD) to have the opportunity to accrue a sizable number of subjects for descriptive purposes. Please refer to Section 9.5 *Study Size* and Section 9.7 *Data Analysis* below.

[figure not shown]
The IBS-C cohort entry date for each cohort member will be defined as the date IBS-C criteria are first fulfilled or 01 February 2013 in Sweden, 13 May 2013 in the UK, and 01 September 2014 in Spain (linaclotide launch dates), whichever is the latest.

The follow-up period for each study subject in the IBS-C cohort will be from the cohort entry date to the earliest of the following (end of follow-up date; one day is the minimum follow-up (Figure 1):

- End of the study period
- Disenrollment from the database (date of transfer out of the practice or the PCP or Sweden)
- Date of last data collection for the practice
- Death
- Index date

The baseline period is the ≥ 12 -month period before IBS-C cohort entry date.

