9.3.3 IBS DIAGNOSIS AND SEVERITY DEFINITION

The target indication of linaclotide is the treatment of moderate-to-severe IBS-C in adults. There are several Read, SNOMED, ICD-9, or ICD-10 codes related to IBS.

GP testimonies gathered during our pilot study, suggests that patients with IBS are frequently assigned IBS codes after other diagnosis have been ruled out and not necessarily during initial consultations, consistent with published research (Harkness EF et al., 2013a and b). Instead, codes of abdominal pain and other abdominal symptoms, suggestive of IBS, and codes of abdominal examinations were mentioned as part of the codes used for these patients. Sometimes, confirmed diagnosis of IBS might not be coded as such and might only remain in the patient's record's notes.

In order to identify potential cases of IBS-C patients using codes, specific IBS-C codes and a combination of an IBS code with a code for constipation will be used. A combination of a code for abdominal pain and at least two abdominal unspecific codes, in addition to a code for constipation will also be used to identify potential cases of IBS-C. [Table 4](#), [Table 5](#) and [Table 6](#) in Annex 3 include a broad list of Read codes, ICD-10, and ICD-9 codes for the identification of patients with IBS with different levels of specificity, as well as codes for constipation to be used in combination.

There are no Read, ICD-9, or ICD-10 codes to indicate the severity of IBS. The most studied and most commonly used tools for measuring IBS severity involve quality-of-life and patient-reported symptom metrics that are not routinely recorded in the computerised databases selected for this study.

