9.5 STUDY SIZE

If we assume a combined population in the UK, Sweden, and Spain of approximately 120 million people (Eurostat, 2014), a prevalence of IBS recorded in primary care of 3.5% (Harkness et al., 2013) and roughly one-third of those corresponding to IBS-C (Tillisch et al., 2005), then the three proposed databases could be expected to include around 216,000 active IBS-C patients. By December 2016, it was estimated that approximately 9,665 patients would have been exposed to linaclotide in the three target databases, for a combined exposure of more than 4,572 patient-years, with the UK contributing approximately 28% of patients, Spain 25%, and Sweden 47%. These estimated number of patients exposed to linalcotide is now expected to be reached by end of December 2017, so the data collection period has been extended accordingly.

Linaclotide clinical trial results (12 and 26 weeks in length) suggest that about 3% of IBS-C patients exposed to placebo and 19.6% of IBS-C patients exposed to linaclotide will experience diarrhoea over those periods, predominantly within the first weeks of initiating therapy. Among them, 4% in the placebo group and 10.1% in the linaclotide-exposed group will experience severe diarrhoea. Therefore, severe diarrhoea was experienced by 0.13% of all IBS-C patients exposed to placebo and by 1.99% of IBS-C patients exposed to linaclotide (Chey et al., 2012; Rao et al., 2012). Other treatments for patients with IBS-C are also associated with diarrhoea, usually of mild severity (Wood, 2012). Information sent to healthcare professionals by the manufacturer of a drug sometimes prescribed for IBS-C patients in the United States (US) warned of very serious diarrhoea complicated with hypovolaemia, hypotension, and syncope that required admission to the hospital and intravenous therapy in approximately one in 2,500 patients (or 0.04%) (Wooltorton, 2004).

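### The symptom route into the UK IBS-C cohort sets no limit on the time between its codes and accepts a negated pain code, so unrelated complaints years apart can create cohort members

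*Protocol*

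**What the plan says.** Section 9.3.3 of the protocol allows identification of potential IBS-C without an IBS diagnosis code: "A combination of a code for abdominal pain and at least two abdominal unspecific codes, in addition to a code for constipation". Annex 3 puts this into operation for CPRD Aurum. A patient has IBS with any code from the IBS-1 list (Table 7), or "if there is a SNOMED code from IBS 2 code lists AND 2 or more codes from IBS 3 code lists ever". Those who qualify on either route "will be said to have IBS-C if they have any of the codes from" Table 10. The Read rule below Table 4, used for CPRD GOLD, has the same symptom route: one pain or discomfort code, at least two unspecific codes, and a constipation code.

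Section 9.2.1.1 requires the IBS-C criteria to be met "anytime during the study period". It adds that patients who meet them "at the beginning of the study period (see below) will be prevalent IBS-C patients". Section 9.2.1.4 sets the start of follow-up: "The IBS-C cohort entry date for each cohort member will be defined as the date IBS-C criteria are first fulfilled", or the launch date (13 May 2013 in the UK) if that is later. Section 9.2.1.3 matches controls to cases on prevalent or incident status, among other factors.

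**The concern.** Section 9.3.3 explains why symptom codes are used at all: GPs often record abdominal symptoms before they assign an IBS code, or never assign one. That describes a set of symptoms belonging to one condition. The rule as written does not ask that the symptoms belong together. It can be met by isolated complaints collected over a long record, and the chance of meeting it grows with the length of that record.

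The cohort defines the source population for every objective. A member created in this way adds person-time to the incidence of diarrhoea and can be drawn as a case or a control. Such a member's entry date may mark nothing more than the day on which the last of several unrelated codes was entered.

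**Working it through.** No figure in the protocol turns on this rule, so the check is mainly a reading of the text.

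**1. Is there a time link anywhere?**
- Aurum, pain and symptom codes: explicitly none ("if there is a SNOMED code from IBS 2 code lists AND 2 or more codes from IBS 3 code lists ever").
- Aurum, constipation code: no window stated, on either the IBS-1 or the symptom route.
- Read rule, and section 9.3.3: none stated.
- Section 9.2.1.1: the study-period condition concerns when the criteria are met, not how far apart the codes lie. Codes before the study period must count, or nobody could be prevalent at its start. Even if all codes had to fall in the UK study period, May 2013 to November 2023 would still allow a spread of about ten years.
- For comparison, the SCD outcome: section 9.3.2 notes that the complication codes can occur without diarrhoea, and so requires them within 45 days of the diarrhoea diagnosis. The cohort rule combines similarly unspecific codes with no such link.

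**2. The rule applied literally.** Take four Aurum codes: *Epigastric pain* (Table 8) in 1999, *Nausea* (Table 9) in 2006, *Indigestion* (Table 9) in 2012 and *Constipation* (Table 10) in 2016. The patient becomes IBS-C in 2016, 2016 − 1999 = 17 years after the first code, and is an incident member with entry in 2016. Move the constipation code to 2010. The set is then complete in 2012, and the same patient is a prevalent member entering on 13 May 2013.

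**3. The lists.**
- Table 8 (pain) contains *Colicky abdominal pain absent*. In the Read list of Table 4 the corresponding *No abdominal pain* is an exclusion.
- Table 8 also contains pelvic and perineal pain codes.
- *Constipation alternates with diarrhoea* is in both Table 9 and Table 10, so one record can count as an unspecific symptom and as the constipation code.
- *Diarrhoea* (103578017) is in Table 9 and in the diarrhoea list of Table 13, so a diarrhoea record can help to complete cohort membership.

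**4. Why the window matters (direction only).** Suppose unrelated complaints arise independently at yearly rates a (pain), b (unspecific symptom) and c (constipation). The chance of meeting the rule within T years is (1 − e^(−aT)) × (1 − e^(−bT)(1 + bT)) × (1 − e^(−cT)). The rates are assumptions; the protocol gives none.

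| a / b / c | T = 2 | T = 10 |
|---|---|---|
| 0.02 / 0.05 / 0.01 | below 0.001% | 0.16% |
| 0.05 / 0.12 / 0.03 | 0.014% | 3.4% |

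T = 2 is one given two-year period, not a window sliding along the record. Codes that cluster within patients would change all four figures. The table shows only that chance qualification depends strongly on the time allowed.

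**5. Safeguards.** Section 9.3.4 has IBS-C and SCD validated for selected cases and controls, and item 1 of the physician's questionnaire asks the GP to confirm or correct the IBS-C diagnosis. The positive and negative predictive values, however, are defined for the outcome algorithm. The sensitivity analyses of section 9.7.3.1 treat unconfirmed SCD events, not unconfirmed IBS-C. The description of the full cohort, its incidence of diarrhoea and any Cox analysis include members whose IBS-C nobody has checked.

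**The case against.** The breadth is deliberate. Section 9.3.3 says that IBS may be coded late or stay in the notes, and section 7 calls IBS chronic and relapsing, so codes spread over years are compatible with true disease. Any fixed window would lose some true patients, and nothing in the protocol shows that 12 months, say, would classify better. GPs are asked about IBS-C for cases and controls, and section 9.9 admits misclassification. Section 9.2.1.4 reports that UK case identification and the start of validation were completed in Q2 2024. A new main cohort rule would change risk sets, matching status and the questionnaires that apply.

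All of this stands as an argument against rewriting the main rule. It does not justify a negated pain code, and it does not show how far the results depend on the symptom route.

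Two stronger readings are tempting, but the documents do not support them.

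- *Most of the cohort lacks IBS.* Annex 3 gives about 16 million active CPRD patients. With the 3.5% prevalence and one-third share of section 9.5, 16,000,000 × 0.035 / 3 ≈ 187,000 true IBS-C patients would be expected. If more than half of the members were false, CPRD alone would hold over 2 × 187,000 = 374,000. Section 4.8 gives about 329,000 for all three countries, and section 9.5.2 expects more than 200,000 in CPRD (200,000 / 16,000,000 = 1.25%, against 3.5% / 3 = 1.17%). The check is rough: coded IBS-C may be rarer than 1.17%, so false members are not excluded. But these figures give a false majority no support.
- *False members explain linaclotide exposure of 1% to 4% instead of 5%.* Section 4.8 says that the number of linaclotide users was already below target in the 2016 progress report, before Aurum was added. That is a shortfall in users and does not show an inflated denominator.

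**Conclusion.** The point holds as a defect in the cohort definition with a limited remedy. Followed literally, the Aurum and Read symptom routes admit people whose codes have no connection in time, and the Aurum list counts a record of absent pain as pain. For those who complete the set after launch, the last code decides entry date and prevalent or incident status. For those who complete it earlier, entry is the launch date.

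The size cannot be derived from the documents, nor can the direction of any effect on the linaclotide odds ratio. The case-control analysis is better protected than the whole-cohort description, because GPs are asked about IBS-C, but only for selected patients and only to the extent that they reply. The conclusion rests on the wording of the rule and the lists, not on the assumed rates above.

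**What to change.** Keep the main cohort rule and make these changes:

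1. Remove negated entries such as *Colicky abdominal pain absent* from Table 8, and report how many members qualified only through them.
2. Prespecify a sensitivity analysis of the linaclotide odds ratio, and of the incidences that are reported, restricted in the UK to patients with an IBS diagnosis code: IBS-1 in Aurum, or the Read equivalents in GOLD. Leave out the IBS-with-diarrhoea codes in Table 7 (the Read list already excludes its own) and the non-diagnostic entries there, such as adverse reactions to a product, a product name, dietary education and a severity score. The diagnosis code should be on record by the index date (case-control) or the entry date (cohort), so that later coding does not decide membership.
3. Optionally, add a second analysis that requires the symptom-route codes to fall within a stated window.

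The data are already extracted, so the cost is the programming of one or two restricted analyses and a small correction to a code list. The downside is fewer patients and matched sets, hence wider intervals, and the loss of some true but sparsely coded IBS-C patients from the restricted set. That is why it should stand beside the main analysis and not replace it.
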